## Protocol

### Study design and participants

This is a single-center prospective quasi-randomized controlled trial, recruiting children aged 2 to 18 years who require hospitalization for CAP in the Department of Pediatrics, The Lady Davis Carmel Medical Center in Haifa, Israel. The study has been approved by the Carmel Medical Center institutional review board (approval number CMC-0170-16), and a parent has to give a written informed consent before recruitment. Exclusion criteria comprised of children who are hemodynamically unstable or required transfer to an intensive care unit; children with other systemic comorbidities or chronic respiratory diseases, including but not limited to congenital bronchopulmonary malformations, Cystic Fibrosis, immune compromise, genetic malformations, and congenital heart disease (excluding patent foramen ovale and atrial septal defect); children from families unable to comprehend and sign an informed consent form.

To determine the sample size required to establish a difference in the hospitalization duration in the study population, given confidence level of 95% and power of 80%, to detect a difference of 0.8 standard deviation (SD) in hospitalization duration between the intervention group and the control group, a sample size of 26 subjects in each group is needed.

Following a senior doctor's diagnosis of CAP based on the combination of clinical, laboratory and radiological results in the Emergency Department, the criteria for admission included at least one of the following: hypoxemia, dehydration, inability to take oral medications, moderate-to-severe respiratory distress, toxic appearance, complicated pneumonia (such as medium-to-large pleural effusion, empyema, lung abscess, pneumatocele, or necrotizing pneumonia), or failure of oral antibiotic treatment (2,28). All these patients were presumed to have bacterial pneumonia and

were treated with antibiotics though we did not specifically test for viral or bacterial origin.

The hospitalized children are randomly assigned to either the intervention or control group based on their order of arrival in a 1:1 case-control and were treated in separate rooms. Both groups receive comparable medical treatment (as needed intravenous (IV) antibiotics, adequate respiratory support, hydration, pain and antipyretic treatment) and investigations, with the intervention group additionally receiving 15-minute visits from MCs twice daily during the first two days of admission.

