### Study assessments

A doctor's daily case report form (CRF) (Supplementary 1) and a parent CRF (Supplementary 2) must be completed on the first two days of admission. In both groups, the child's primary caregiver, who accompanies them during the hospital stay

should answer the parent CRF. These forms document details of child's treatment, clinical assessment, vital signs, symptoms, and overall well-being as perceived by a parent (regarding respiratory state, mood and vitality) and the treating doctor (regarding pain, mood and vitality). The well-being variables will be evaluated by a visual analogue scale (VAS) in the CRF's grading their opinion between 1 (lowest score) to 10 (best score) except for pain where VAS meaning was 1= not suffering at all to 10 = most suffering.

The primary outcome parameter is length of hospitalization in hours, determined by the duration between admission and discharge from the pediatric department. Secondary outcome parameters include the duration of IV treatment, need for chest tube insertion, changes in well-being scores as reported by both the parent and the treating physician, and alterations in vital signs and laboratory results.

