#### Statistical analysis

Statistical analyses will be performed using IBM statistics (SPSS) vs 24. The continuous variables will be presented by mean and SD or Median and IQR, as appropriate. The categorical variables will be presented in percentages. To check differences between the two groups, Chi square test will be used for the categorical variables and independent t-test, or Mann Whitney for the continuous variables.  $P < 0.05$  is considered statistically significant.

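### The vital-sign outcome has no stated metric and only an unadjusted test across ages 2 to 18; adjusting for baseline and age is a cheap gain in precision of uncertain size

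*Combined protocol and SAP*

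**What the plan says.** The Study design and participants section describes "recruiting children aged 2 to 18 years who require hospitalization for CAP", with allocation 1:1 by order of arrival and no stratification by age. It sizes the trial at 26 per group, "to detect a difference of 0.8 standard deviation (SD) in hospitalization duration". That calculation concerns the primary outcome only.

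Under Study assessments, the secondary outcomes include "alterations in vital signs and laboratory results". The daily forms "must be completed on the first two days of admission", and their content is described as follows: "These forms document details of child's treatment, clinical assessment, vital signs, symptoms, and overall well-being". The text does not name individual vital signs. It also does not say whether the outcome is a within-child change, a percentage change, a daily level, or a classification as normal or abnormal.

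The Statistical analysis section offers "independent t-test, or Mann Whitney for the continuous variables", and chi-square for categorical ones. No covariate, age-specific score or age threshold appears anywhere.

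**The concern.** Heart rate and respiratory rate are the obvious continuous vital signs in pneumonia, and both vary with age in childhood. If levels are compared between arms, the age-related spread from 2 to 18 years goes straight into the error term. If within-child changes are compared, age still matters to the extent that the size of the fall depends on it: a young child who starts from a higher rate may have further to fall. An unadjusted two-sample test leaves that spread in the denominator, although age and the starting value could remove part of it.

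At stake is power for one secondary outcome in a trial of about 52 children. The clowns set out to relax the patients, so vital signs are a plausible place for an effect to appear, and the trial was not sized for them.

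**Working it through.** **The plan's own figure.** A two-sided t-test at the 5% level with 80% power for a 0.8 SD difference needs 25.5 per group, rounded up to 26. Power at 26 per group is 80.7%. The stated size reproduces, but it concerns length of hospitalization and says nothing about vital signs.

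**Inputs from the documents.** Ages 2 to 18; 26 per group; significance at 0.05 (sidedness not stated, two-sided assumed); unadjusted tests.

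**Inputs assumed.** Age uniform over 2 to 18; the fall in respiratory rate over the two days linear in age; within-age SDs as given below. None of these is in the documents.

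**Step 1: age spread.** SD of age = 16/√12 = 4.62 years, variance 21.33. The SD of the arm difference in mean age is 4.62 × √(2/26) = 1.28 years.

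**Step 2: share of the variance of the change explained by age.** Share = slope² × 21.33 / (slope² × 21.33 + within-age variance).

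- Steep case: the fall goes from 20 breaths/min at age 2 to 8 at age 18, with within-age SD 5. Slope = 12/16 = 0.75 per year. Share = 12.0/(12.0 + 25) = 0.32.
- Moderate case: the fall goes from 15 to 8, with within-age SD 6. Slope = 7/16 = 0.44 per year. Share = 4.1/(4.1 + 36) = 0.10.
- Alternative model: assumed normal heart rate falls from 110 to 75 and respiratory rate from 28 to 16 over the age range, with residual SDs of 8 to 16 and 3 to 7. Simulation gives a share of 0 if recovery is the same absolute amount at every age, and about 0.01 to 0.07 if it is proportional to the child's normal value.

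**Step 3: power at 26 per group for an effect of 0.6 SD of the unadjusted outcome.** Removing the age share raises the standardised effect to 0.6/√(1 − share).

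| Age share | Standardised effect | Power |
|---|---|---|
| 0 | 0.600 | 56.4% |
| 0.01 | 0.603 | 56.8% |
| 0.07 | 0.622 | 59.5% |
| 0.10 | 0.633 | 61.0% |
| 0.32 | 0.730 | 73.3% |

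These figures ignore the one degree of freedom spent on age, and they count no gain from adjusting for the baseline value.

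**Step 4: if day-specific levels are compared.** In the same simulation, age explains about 0.196 to 0.658 of the variance of the day-2 level. The standard error of the unadjusted comparison is then larger by a factor 1/√(1 − share): 1/√0.804 = 1.12 to 1/√0.342 = 1.71, an inflation of 12% to 71%.

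**Step 5: chance age imbalance.** A 1-SD imbalance in mean age shifts the arm difference by 0.75 × 1.28 = 0.96 breaths/min (steep case) or 0.44 × 1.28 = 0.56 (moderate case). The standard error of the unadjusted difference is √37.0 × √(2/26) = 1.69 or √40.1 × √(2/26) = 1.76. The shift is one component of that standard error, not an addition to it.

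**The case against.** The strongest reply is that the plan never says raw changes are used. The metric is simply unstated; heart rate and respiratory rate are not named; and the chi-square provision leaves room for coding each value as normal or abnormal for age. The physician's form, which might list the items, is a supplement that is not part of the text reviewed. This stands: a reader may infer a test on raw units from the plan's silence, but the documents do not state it.

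The second reply is that a within-child change already cancels the child's stable age-related level, so different normal rates at different ages do not by themselves mix age with recovery. This also stands. Only age-dependence of the change itself matters, and under the proportional model its share is at most about 7%, which inflates the standard error by about 4%.

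The third concerns a tempting stronger reading: that, with 26 per group, the vital-sign result may merely reflect an age difference between the arms. The documents do not support it. Allocation by order of arrival is not tied to age, and the ordinary standard error allows for chance imbalance, so the 5% error rate is not raised. Precision loss and chance shift are the same variance described twice.

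What survives is narrower. The outcome needs a defined metric, and the unadjusted test passes over information already in hand.

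**Conclusion.** The point holds as one about definition and efficiency for a secondary outcome. The plan fixes no metric for the vital-sign alterations and uses neither age nor the starting value in their analysis.

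The size cannot be derived from the documents. For within-child change, an age share of 0 to 10% means that power for a 0.6 SD effect goes from 56% to somewhere between no gain and about 61%. The rise to 73% requires a fall that depends steeply on age (a 32% share) and should be read as an upper illustration for change scores. If day-specific levels are compared, which the text does not rule out, the loss is larger: 12% to 71% on the standard error under the assumed values. All of these rest on uniform age and on assumed slopes and SDs.

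The unadjusted comparison remains valid with respect to age, and the primary outcome is untouched. Acting on this is a cheap improvement and not a condition for the trial's validity.

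**What to change.** In the Statistical analysis section, list the continuous vital signs to be analysed. State that, for each, the day-2 value will be analysed in a linear model with arm, baseline value and age, reporting the adjusted arm difference with a 95% CI. Fix this wording before the data are analysed.

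Define the baseline as a value recorded before the first clown visit. Visits take place on both of the first two days, so a day-1 form value may already reflect the intervention, and adjusting for it could remove part of the effect. If the day-1 value cannot be shown to precede the first visit, use the admission value or adjust for age alone.

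A change in age-specific z-score is a less suitable route. It needs an outside reference chart that the plan does not name, and it need not remove age-dependence of the change.

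Cost: one or two sentences in the plan and slightly more analysis work. Age is needed for eligibility and vital signs are already on the forms; the only possible addition is confirming the time of the baseline reading. The result is an adjusted difference, which is a little less direct to read than a raw one.

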#### Statistical analysis

Statistical analyses will be performed using IBM statistics (SPSS) vs 24. The continuous variables will be presented by mean and SD or Median and IQR, as appropriate. The categorical variables will be presented in percentages. To check differences between the two groups, Chi square test will be used for the categorical variables and independent t-test, or Mann Whitney for the continuous variables.  $P < 0.05$  is considered statistically significant.
